6.2 Pharmacokinetics

Pharmacokinetic analysis will be performed on the PK Population respectively

Plasma samples will be analyzed for digoxin concentrations using a validated method.

PK plasma samples will be collected at the following time points: pre-dose of digoxin (0 h) and 0.5, 1, 1.5, 2, 3, 4, 6, 8, 12, 24, 48, 72, 96, and 120 h post dose of digoxin.

6.3 Safety

Safety analysis will be performed on the Safety Population.

The safety profile of digoxin will be assessed through the recording, reporting, and analyzing of adverse events, clinical evaluations, and laboratory tests.

Safety variables include the following:

1. Adverse events
2. Clinical laboratory measurements – serum chemistry, hematology, and urinalysis
3. Urine drug screen
4. Vital signs
5. ECG
6. Physical examination
7. Pregnancy test
8. Concomitant medications/treatments

6.3.1 Study Day and Visit Window Definitions

Refer to section 6.1.1 for details.

6.3.2 Extent of Exposure to Study Medication

Subjects who gave consent to participate in the study will be randomly assigned to 1 of the 2 treatment groups (Group 1 and Group 2). Each treatment group will receive 2 treatments (Treatment A and Treatment B) in a different order during each of the treatment periods (Period 1 and Period 2). The duration of

Treatment A is 9 days and Treatment B is 7 days. Subjects will remain in the clinic for 16 days during the entire study. Subjects will be out of the clinic between the 2 treatment periods for 9 days for Group 1 and 7 days for Group 2. Overall, each study subject will receive 8 single oral doses of 20 mg bexagliflozin tablets and 2 single oral doses of 0.5 mg digoxin in each treatment period. The duration of the overall study from screening until study termination is to be a maximum of 46 days.

6.3.3 Adverse Events (AEs)

Adverse events will be collected and coded using version 20.1 Sept 2017 (or newer) of MedDRA. Analysis of adverse events will be carried out on the Safety Population. All adverse events will be included in the individual subject data listings. Only treatment emergent adverse events (TEAEs) will be tabulated in summary tables. The incidence of TEAEs will be presented by treatment. If the AE(s) onset date-time or date occurs after the first dose up until right before the first dose in the second treatment period, the AE(s) will be assigned to the first treatment period. If the AE(s) onset date-time or date occurs after the first dose in the second treatment period, the AE(s) will be assigned to the second treatment period. A similar approach will be used with respect to all subsequent treatments.

All adverse events will be assessed by the investigator(s) with respect to severity, relationship to study drug and seriousness.

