6.7.1 Collecting and Reporting Adverse Events

Adverse event collection will begin on the first clinical admission day. The investigator will periodically assess subjects for the occurrence of adverse events. To avoid bias in collecting information about adverse events, the investigator should ask subjects the following question: "How have you felt since you were last checked?" All adverse events (serious and non-serious) reported by the subject must be recorded on the source documents and CRFs provided by the sponsor.

In addition, Theracos' Medical Monitor or its designated personnel must be notified immediately by telephone or fax of any immediately reportable adverse events according to the procedure outlined below. Special attention should be paid to recording hospitalization and concomitant medications.

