9.6.1 Adverse Events

Adverse events will be mapped to preferred term and body system using the Medical Dictionary for Regulatory Activities (MedDRA). The number and percentage of subjects reporting adverse events will be determined by relationship to treatment and by severity of the event. Drug-related adverse events will be considered those to be possibly related to bexagliflozin administration.

Adverse event listings will be provided for the following subsets:

- all treatment emergent AEs (TEAEs).
- all TEAEs at least possibly related to bexagliflozin.
- serious TEAEs (if any).
- TEAEs leading to study discontinuation (if any).

AEs are dosing emergent if they occur on or after bexagliflozin administration. TEAEs will be considered at least possibly related to bexagliflozin based on the investigator's assessment. Only TEAEs will be tabulated in summary tables. If the AE(s) onset date-time or date occurs after the first dose up until right before the next dose, the AE(s) will be assigned

to the first treatment. Any AE(s) that occur after the second dose up until the follow-up visit will be assigned to the second treatment.

Tabulations will display TEAEs by severity and relationship to bexagliflozin.

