6.3.3.1 Treatment-Emergent AE (TEAE)

An adverse event is considered treatment-emergent if it occurs after digoxin and/or bexagliflozin administration and if the date –time or date of onset is on or after the date of first dose of study medication, or worsens during the treatment period (intensity/severity grades worsen).

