6.3.3.4 Adverse Events Counting Rules

1. A subject with more than one different AE in a particular system organ class (SOC) will be counted only once in the total of subjects experiencing adverse events in that particular SOC.
2. A subject having experienced the same event (AE preferred term) more than once during the study will be counted only once in the number of subjects with that event.
3. A subject having experienced the same event (AE preferred term) more than once during the study with a different severity or seriousness, it will be counted only once with the worst grade and seriousness respectively.
4. A subject having experienced the same event (AE preferred term) more than once during the study with a different causal relationship to the study drug, it will be counted only once by considering the most-related documented degree of relationship.

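### The SAP counts worsening as treatment-emergent but assigns events to treatment by onset only, so an event that starts before the first Period 2 dose and worsens after it is tabulated under the Period 1 treatment

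*SAP*

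**What the plan says.** **What makes an event treatment-emergent.** SAP 6.3.3.1 has two routes. One is onset on or after the first dose. The other is a rise in grade: "or worsens during the treatment period (intensity/severity grades worsen".

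**What places it in a column.** SAP 6.3.3 tabulates only treatment-emergent events and states "The incidence of TEAEs will be presented by treatment". Two sentences set the period, and so the treatment. The Period 1 sentence begins "If the AE(s) onset date-time or date occurs after the first dose up until right before the first dose in the second treatment period". The Period 2 sentence begins "If the AE(s) onset date-time or date occurs after the first dose in the second treatment period". Both use onset and neither mentions worsening.

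**When collection starts.** Protocol 6.7.1: "Adverse event collection will begin on the first clinical admission day". That day is Day 0, and the first dose is on Day 1. AEs are also assessed on the Period 2 admission day (Day 18 in Group 1, Day 14 in Group 2), the day before Period 2 dosing starts.

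**Counting.** For a repeated term with differing severity, SAP 6.3.3.4 says "it will be counted only once with the worst grade and seriousness respectively". It works per study and names no treatment column.

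**Protocol.** Section 9.6.1 has no worsening route ("AEs are dosing emergent if they occur on or after bexagliflozin administration") and also assigns by onset ("If the AE(s) onset date-time or date occurs after the first dose up until right before the next dose").

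**The concern.** The definition and the assignment rule do not use the same event date. An event can enter the tables because of something that happened under one treatment and be placed by something that happened under the other, or before either.

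The secondary objective is the safety and tolerability of digoxin when co-administered with bexagliflozin, and the by-treatment TEAE summaries in SAP 8.4.1 are a main output for it. A complaint that is mild before Period 2 and becomes moderate on the combination is relevant to that objective. For Group 2 the stated rule reports it in the comparator column.

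**Working it through.** No figure in the plan depends on this point, so there is none to reproduce. The check applies SAP 6.3.3.1 and 6.3.3 together to each combination of onset and worsening, with A = bexagliflozin plus digoxin and B = digoxin alone.

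| Onset | Worsens | Column under SAP 6.3.3 | Treatment at worsening |
|---|---|---|---|
| Period 1, after dosing | Period 1 | Period 1 treatment | Same: correct |
| Period 1, gap, or Period 2 admission day; Group 1 (A then B) | After first Period 2 dose | A | B: other column |
| Period 1, gap, or Period 2 admission day; Group 2 (B then A) | After first Period 2 dose | B | A: other column |
| Day 0, before any dose | Period 1 or 2 | Neither sentence applies | Period 1 or 2 treatment: no column |
| After first Period 2 dose | Period 2 | Period 2 treatment | Same: correct |

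An event need not last through the 7- or 9-day gap to fall in rows 2 and 3, because one starting on Day 14 or Day 18 qualifies.

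**Does another rule repair it?** SAP 6.3.3.4 and 8.4.1 keep the highest grade but do not say where it goes. SAP 6.3.3.7 imputes partial start and end dates, not dates of worsening. Protocol 9.6.1 also goes by onset. Neither document tells sites to open a new record when severity rises.

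**Size.** Inputs: 18 subjects, 1:1 to the two sequences (SAP 3.2), all assumed to be dosed in both periods, so each column has a denominator of 18.

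- Any-grade row, event kept in its onset column and also counted where it worsened: the second column gains 1/18 = 5.6 percentage points and the first is unchanged. The A-B difference changes by 5.6 points, or by 0 if the subject is already counted in that row of the second column.
- Day 0 event that worsens: one column gains 1/18 = 5.6 points.
- Table in which the event leaves one column for the other, as the worst grade would in a severity table: 2/18 = 11.1 points.
- With 0 to 2 subjects (assumed), the any-grade difference changes by 0 to 2/18 = 11.1 points. The upper end needs both cases to run the same way; one in each sequence would cancel.

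**The case against.** **Worsening may be entered as a new AE line.** Its onset would then be the date of worsening, and SAP 6.3.3 would work as written. The counting rules, which allow the same term to recur with different severities, are compatible with that practice. SAP 1 says the plan is to be read with the CRFs, which are not available here. This stands as a possibility, but nothing in the two documents requires it.

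**The Day 0 case depends on how SAP 6.3.3.1 is parsed.** If its opening condition, occurrence after administration, also governs the worsening clause, a Day 0 event is never treatment-emergent and nothing is dropped. The wording permits this. It would leave the clause with no work to do, since an event occurring after dosing already qualifies by onset, so the other reading is more natural. The Period 2 case does not depend on the parse.

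**The effect is narrow and two-sided.** This stands. A reader might infer that the rule systematically hides harm from the combination. The documents do not support that: within-period worsening is placed correctly, only events already present before the first Period 2 dose can cross over, and with 1:1 sequences the error runs in both directions. Nor is anything lost from the report, because all AEs are listed.

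**Conclusion.** The defect holds in a limited form. It goes beyond missing detail: followed literally, SAP 6.3.3 gives the wrong column for an event that starts before the first Period 2 dose and worsens after it. On the more natural reading of 6.3.3.1, it gives no column for a Day 0 event that worsens.

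The effect is at most 5.6 percentage points per subject on an any-grade difference. A reader might take 11.1 points per subject as the general figure. It applies only where the event moves from one column to the other; in an incidence table the onset column properly keeps the event.

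This rests on 18 subjects dosed in both periods, on an assumed 0 to 2 cases, and on worsening not already being recorded as a separate event. Only descriptive safety counts for the secondary objective are affected. It is worth correcting before database lock.

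**What to change.** In SAP 6.3.3, add that:

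- a TEAE that qualifies by a rise in severity is assigned to the treatment period in which severity rose (a Day 0 event that worsens in Period 1 goes to the Period 1 treatment);
- an event with post-dose onset stays in its onset period at its original grade, and is also counted at the higher grade in the later period if it worsens there.

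In SAP 6.3.3.4 and 8.4.1, apply the worst-grade rule within treatment.

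The cost is a few sentences and one derived variable. The change also needs the date-time of worsening, for example through a new AE line when severity rises, and a continuing event then takes two lines. If the CRF does not capture this, a completion note is needed. One might assume no new data are required, but the documents do not establish that. The annotated CRFs were already final when the SAP was written, and an SAP edit cannot derive a date that was never recorded.

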This is a phase 1, single center, open-label, two-period, two-treatment, crossover study to evaluate the effect of bexagliflozin tablets, 20 mg, on the pharmacokinetics (PK) of digoxin, 0.5 mg, when co-administered in healthy subjects. Approximately 18 eligible healthy subjects will be randomized to one of the two groups (Group 1 and 2) with up to 9 subjects per group. Subjects will reside in the clinic for a total of 16 days, divided into two treatment periods, Periods 1 and 2. Subjects will be discharged and out of the clinic between the 2 treatment periods for 9 days for Group 1 and 7 days for Group 2. During the treatment periods, subjects will receive 2 treatments in differing order: Treatment A, bexagliflozin administered once daily for 8 days with digoxin co-administered on Day 3 and Treatment B, digoxin administered alone on Day 1. Safety monitoring will be conducted throughout the study.

Group 1:

Period 1, Treatment A: Subjects randomized to Group 1 will be admitted to the clinic on Day 0. Starting on Day 1, subjects will receive once daily oral dose of 20 mg bexagliflozin for 8 days; a single dose of 0.5 mg digoxin will be co-administered with bexagliflozin on Day 3. Blood samples for PK will be drawn at pre-dose and at 0.5, 1, 1.5, 2, 3, 4, 6, 8, and 12 hours (h) on Day 3, 24 h (Day 4), 48 h (Day 5), 72 h (Day 6), 96 h (Day 7), and 120 h (Day 8) after administration of digoxin. Subjects will be discharged on Day 8.

Period 2, Treatment B: Subjects will be admitted on Day 18 and receive a single oral dose of 0.5 mg digoxin on Day 19. Blood samples for PK will be drawn at pre-dose and at 0.5, 1, 1.5, 2, 3, 4, 6, 8, and 12 hours (h) on Day 19, 24 h (Day 20), 48 h (Day 21), 72 h (Day 22), 96 h (Day 23), and 120 h (Day 24) after administration of digoxin. Subjects will be discharged from the clinic on Day 24.

Group 2:

Period 1, Treatment B: Subjects randomized to Group 2 will be admitted to the clinic on Day 0. On Day 1, subjects will receive a single oral dose of 0.5 mg digoxin. Blood samples for PK will be drawn at pre-dose and at 0.5, 1, 1.5, 2, 3, 4, 6, 8, and 12 hours (h) on Day 1, 24 h (Day 2), 48 h (Day 3), 72 h (Day 4), 96 h (Day 5), and 120 h (Day 6) after administration of digoxin. Subjects will be discharged on Day 6.

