8.4.1 Adverse Events

All AEs will be coded to system organ class (SOC), and preferred term (PT), using the latest Medical Dictionary for Regulatory Activities coding dictionary (version to be specified in the clinical study report). All reported AEs will be listed, but only TEAEs will be summarized.

The incidence of all TEAEs will be summarized by treatment. In the summary tables, subjects may be counted under multiple SOCs and PTs, but for each SOC and PT, subjects are only counted once. If a subject has the same AE on multiple occasions, the highest severity (severe > moderate > mild) or drug relationship (definite > probable > possible > not likely related > unrelated) recorded for the event will be presented. If severity is missing, subjects will be included as missing (for severity). If drug relationship is missing, subjects will be included in related tables (e.g., considered related). Summary tables will be organized by SOC, then PT.

The following summaries will be presented for TEAEs:

- Overall Summary of TEAEs by Treatment
- Incidence of TEAEs by Treatment, System Organ Class, and Preferred Term
- Incidence of Treatment Emergent Serious Adverse Events by Treatment, System Organ Class, and Preferred Term

Subjects who prematurely discontinued due to TEAEs and subjects with serious TEAEs will be listed.

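### The AE assignment rule gives Treatment A more observation time than Treatment B (225 vs 171 subject-days if collection ends at discharge), so the by-treatment TEAE table is expected to lean modestly against co-administration

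*SAP*

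**What the plan says.** SAP 6.3.3 has a two-part rule. An AE whose onset "occurs after the first dose up until right before the first dose in the second treatment period" belongs to the first period. One that "occurs after the first dose in the second treatment period, the AE(s) will be assigned to the second treatment period". No end is given for the second window. Each period holds one treatment, so assigning an AE to a period assigns it to a treatment. SAP 6.3.3 then states: "The incidence of TEAEs will be presented by treatment". SAP 8.4.1 repeats this ("The incidence of all TEAEs will be summarized by treatment") and lists tables by treatment. Neither section mentions a common window, an exposure-adjusted rate or time at risk.

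The day grid is in SAP Section 1. For Group 1 in Period 1 (Treatment A): "Starting on Day 1, subjects will receive once daily oral dose of 20 mg bexagliflozin for 8 days", with digoxin added on Day 3. For Period 2 (Treatment B): "Subjects will be admitted on Day 18 and receive a single oral dose of 0.5 mg digoxin on Day 19", and "Subjects will be discharged from the clinic on Day 24". Group 2 takes digoxin alone on Day 1, starts bexagliflozin on Day 15, takes digoxin on Day 17 and leaves on Day 22. Subjects are "out of the clinic between the 2 treatment periods for 9 days for Group 1 and 7 days for Group 2".

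**The concern.** The Period 1 window takes in the whole interval out of clinic, and the Period 2 window has no matching interval. In a balanced crossover one might expect this to cancel between treatments, but it does not. Treatment A opens with two bexagliflozin days before digoxin in both groups, and the gap that follows A in Group 1 is two days longer than the gap that follows B in Group 2. A is therefore observed longer than B in either position.

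The secondary objective is the safety and tolerability of digoxin when given with bexagliflozin, and the by-treatment TEAE tables are the planned AE summary that sets the two treatments side by side. A reader of those tables could not see that one column had more observation time than the other, and could take a small excess under A as a signal.

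**Working it through.** **Check of the day grid.** Full days out of clinic = readmission day − discharge day − 1. Group 1: 18 − 8 − 1 = 9. Group 2: 14 − 6 − 1 = 7. Both match the SAP.

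**Windows under the SAP rule.** A Period 1 window runs from the first dose to the first Period 2 dose. A Period 2 window is taken to run from the first dose to discharge, the last AE assessment in Protocol Appendix 1.

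| | Group 1 | Group 2 | Sum |
|---|---|---|---|
| A | 19 − 1 = 18 d | 22 − 15 = 7 d | 25 d |
| B | 24 − 19 = 5 d | 15 − 1 = 14 d | 19 d |

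With 18 subjects allocated 1:1 (SAP 3.2), all completing: A 9 × 25 = 225 subject-days, B 9 × 19 = 171; 225/171 = 1.32.

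**Source of the 6 extra days per pair of subjects (25 − 19).** The two-day bexagliflozin lead-in in each group gives 4. The longer gap after A (9 vs 7 days) gives 2.

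**Other ways of drawing the windows.**

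| Window | A (Groups 1, 2) | B (Groups 2, 1) | Ratio |
|---|---|---|---|
| SAP rule, Period 2 to discharge | 18, 7 | 14, 5 | 1.32 |
| Discharge day counted in Period 2 | 18, 8 | 14, 6 | 1.30 |
| 14-day SAE monitoring added to Period 2 | 18, 21 | 14, 19 | 39/33 = 1.18 |
| Start at digoxin dose, keep washout | 16, 5 | 14, 5 | 21/19 = 1.11 |
| First dose to discharge in each period | 7, 7 | 5, 5 | 1.40 |
| Digoxin dose to 120 h | 5, 5 | 5, 5 | 1.00 |

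The fifth row shows that dropping the washout alone does not equalise the treatments.

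**Expected incidence with no drug effect.** Assume one constant rate h per subject-day under both treatments, in and out of clinic. The documents give no rate, so a range is shown. The expected proportion with at least one TEAE is the mean over the two groups of 1 − exp(−h × days).

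- h = 0.01: A (0.165 + 0.068)/2 = 11.6%; B (0.131 + 0.049)/2 = 9.0%. Difference about 2.6 points × 18 = 0.5 subjects.
- h = 0.02: 21.6% vs 17.0%, about 0.8 subjects.
- h = 0.03: A (0.417 + 0.189)/2 = 30.3%; B (0.343 + 0.139)/2 = 24.1%. Difference 6.2 points × 18 = 1.1 subjects.

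Over a wider range of 0.005 to 0.10 per day the expected excess is about 0.3 to 1.7 subjects. Simulation over that range, treating the two windows as independent, puts A above B in 41% to 68% of trials and below B in 20% to 29%; the rest are ties.

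**The case against.** The strongest reply is that most of the difference is Treatment A itself. The SAP defines A as eight days of bexagliflozin with digoxin on the third, so events on the two lead-in days properly belong to A. This stands. Those days are 4 of the 6 extra days, and without them the ratio is 1.11. A reader might infer from the 1.32 that the whole gap is an artefact of observation time; the SAP's definition of A does not support that.

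Second, the SAP does not say that the Period 2 window closes at discharge. Protocol 9.6.1 runs it to a follow-up visit, which is undated and held only if clinically indicated (Protocol 7.4). Protocol 6.7.4.2 requires active SAE monitoring for at least 14 days after discharge. It would therefore be wrong to say that Period 2 treatments cannot collect any out-of-clinic events: they can for SAEs, and counting that tail lowers the ratio to 1.18. For non-serious AEs the asymmetry remains. Subjects are asked at readmission how they have felt since they were last checked (Protocol 6.7.1), and no such routine contact follows Period 2.

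Third, the tables are descriptive. SAP 3.3 plans no hypothesis testing, all AEs are listed, safety also rests on laboratory tests, vital signs, ECGs and examinations, and SAP 6.3.2 states the unequal treatment durations openly. This also stands: no error rate is affected. It does not give the reader of the TEAE table the time at risk behind each column.

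Fourth, clustering of AEs soon after digoxin, or poor recall of events at home, would shrink the excess. That is fair, and the constant rate is only an assumption.

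**Conclusion.** The concern holds in a limited form. SAP 6.3.3 gives the two treatments unequal AE windows and neither 6.3.3 nor 8.4.1 allows for it. A has more observation time in every version of the rule checked, except the window from digoxin dose to 120 h, which equalises it. The ratio is 1.32 if collection ends at discharge, 1.18 with the SAE tail and 1.11 from the digoxin dose.

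A reader might conclude that the table would show an excess for the combination whatever the truth. The figures support only an expected lean of about 0.5 to 1.1 subjects of 18 at assumed rates of 0.01 to 0.03 per day, and B could well come out equal or higher. These sizes rest on 9 completers per group, an equal and constant background rate, and equal capture in and out of clinic. The point bears on how the secondary safety objective is read and leaves the pharmacokinetic analysis untouched. It is worth correcting because the correction is cheap.

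**What to change.** In SAP 6.3.3 and 8.4.1:

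1. Keep the planned full-window TEAE table. State when the Period 2 window closes, and print subject-days at risk under each treatment heading.
2. Add a table limited to the interval from digoxin dose to the 120 h sample: Days 3 to 8 and 17 to 22 for A, Days 1 to 6 and 19 to 24 for B. Each cell is 5 days in clinic, 90 vs 90 subject-days. Base the A-versus-B comparison on this table.
3. Tabulate separately the events before digoxin in A and the events after 120 h in either treatment. Leave the full listing unchanged.

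The cost is SAP wording and flags derived from dates already collected; no visit or procedure changes.

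The downside is real. The equal-window table holds 180 of 396 subject-days, about 45%. It omits A's lead-in days and late events, including those after the last bexagliflozin dose on Day 8 or 22 that follow the 120 h sample. At the protocol's digoxin half-life of about 35 h, 120 h is 120/35 = 3.4 half-lives, so roughly 9% of the drug remains and later events are not plainly off treatment. For these reasons the new table should sit beside the full table and not replace it.
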